6.2.3.6 Change in QLI-SCI III

The Ferrens and Powers Quality of Life Index – Spinal Cord Injury (QLI-SCI) III will be assessed (Appendix J of the protocol) at discharge and at months 1, 2, 3, 6, and 12. QLI-SCI III results at discharge will be used as the reference time point (baseline) to assess changes in subjects' quality of life at months 1, 2, 3, 6, and 12. QLI-SCI contains two parts that measure the satisfaction (1=Very Dissatisfied to 6=Very Satisfied) and importance (1=Very Unimportant to 6=Very Important) with 37 aspects of quality of life. Importance ratings are used to weight satisfaction responses, so that scores reflect satisfaction with the aspects of life that are valued by the individual. The QLI produces five scores: quality of life overall and in four domains (health and functioning, social and economic domain, psychological/spiritual domain, and family). The scores are calculated as follows:

Subscale Scores:

The subscale questions are distributed as follows:

Health and Functioning Subscale:

- 1. Health
- 2. Health care
- 3. Pain
- 4. Energy (fatigue)
- 5. Ability to take care of yourself
- 6. Ability to go places
- 7. Ability to clear lungs
- 8. Control over life
- 9. Chances for living as long as you would like
- 14. Sex life
- 20. Ability to take care of family responsibilities
- 21. Usefulness to others
- 22. Worries
- 29. Things for fun

- 30. Chances for a happy future

Social and Economic Scale:

- 17. Friends
- 19. Emotional support from people other than your family
- 23. Neighborhood
- 24. Home
- 25/26. Job/Not having a job
- 27. Education
- 28. Financial needs

Psychological/Spiritual Subscale:

- 31. Peace of mind
- 32. Faith in God

- 33. Achievement of personal goals
- 34. Happiness in general
- 35. Life satisfaction in general
- 36. Personal appearance
- 37. Self

Family Subscale:

- 10. Family health
- 11. Children
- 12. Ability to have children
- 13. Family happiness
- 15/16. Spouse, lover, or partner/Not having a spouse, lover, or partner
- 18. Emotional support from family

For each of these four subscales, the score is calculated as follows:

- 1) Recode satisfaction scores: To center the scale at zero, subtract 3.5 from satisfaction response for each item (this will produce responses of -2.5, -1.5, -0.5, +0.5, +1.5, +2.5).
- 2) Weight the satisfaction responses with the paired importance responses: multiply the recoded satisfaction response by the raw importance response for each pair of items.
- 3) Obtain preliminary sum for the subscale score: Add the weighted responses from step 2 together for each corresponding subscale item.

- 4) Obtain final subscale score: Divide the preliminary sum from step 3 by the number of complete item pairs answered in each corresponding subscale (this prevents bias from missing data). To eliminate negative numbers in the final score, add 15 to each score. Each final subscale score will have a range of 0-30, where 30 is the highest quality of life and 0 is the lowest quality of life.

Overall QLI-SCI III Score:

The calculation for the overall (total) QLI-SCI III Score is similar to the subscales:

- 1) Recode satisfaction scores: To center the scale at zero, subtract 3.5 from satisfaction response for each item (this will produce responses of -2.5, -1.5, -0.5, +0.5, +1.5, +2.5)
- 2) Weight the satisfaction responses with the paired importance responses: multiply the recoded satisfaction response by the raw importance response for each pair of items
- 3) Obtain preliminary sum for the overall total score: Add the weighted responses from step 2 together.
- 4) Obtain final overall total QLI-III score: Divide the preliminary sum from step 3 by the total number of complete item pairs answered. To eliminate negative numbers in the final score, add 15 to each score. This final overall total QLI-III score will have a range of 0-30, where 30 is the highest quality of life and 0 is the lowest quality of life.

QLI-SCI III total score and subscale scores will be calculated for each subject at hospital discharge and at months 1, 2, 3, 6, and 12. Change from baseline (Hospital Discharge) in SCIM III will also be derived at each post baseline time point. QLI-SCI III total score, subscores, change from baseline for total score and subscores will be tabulated by subject and summarized overall at each time point.

Subjects with improvement, worsening, and no change from baseline in their quality of life as determined by their QLI-SCI III assessments will be tabulated. Improvement will be defined as an increase in QLI-SCI III score/subscore from baseline, while worsening will be defined as a decrease in score/subscore.

6.3 Safety Analysis

Safety analysis will be performed using all subjects in the Safety Population Excluding Screen Failure Subjects. The safety data will be presented descriptively and no formal statistical analyses are planned. The following sections provide the safety presentations for the Safety Set Excluding Screen Failure Subjects.

The primary safety analysis of the study will be presented upon completion of the 6 Month Primary Endpoint Follow-up Visit (6 Months post-Scaffold) for the subjects in the Safety Set Excluding Screen Failures.

Additional safety Analysis may be performed for information obtained after the 6 Month Primary Endpoint Follow-up Visit (12 month and 24 month post-Scaffold follow-up visits) upon the completion of collection of clinical data, as needed.

6.3.1 Extent of Exposure

The Scaffold is a bioresorbable material, and based upon pre-clinical testing, is expected to be completely cleared from the site of implant within four to eight weeks. A summary of study participation will be provided but no analysis of extent of exposure is applicable for this study.

6.3.2 Safety Events

The Medical Dictionary for Regulatory Activities (MedDRA) (Version 17) [5] will be used to classify all safety events (AEs, ADEs, Safety Events of Interest [associated with the potential risk with the use of Scaffold, risk associated with neurological procedures, and general risks of surgery and spinal surgery] SAEs, SADEs and UADEs) with respect to system organ class (SOC) and preferred term (PT). ADEs will be considered any safety event that is at least possibly related to the Scaffold or the procedure to implant the Scaffold. The safety event dataset will be reviewed by the study team to identify all events and to group the identified events into different categories for the analysis, particularly the Safety Events of Interest.

Summary tables will provide the total number of safety events of each type (AEs, ADEs, Safety Events of Interest, SAEs, SADEs and UADEs, Safety Events Leading to Discontinuation) and the number and proportion of subjects with each type of safety event.

Events will be tabulated for the overall study period and separately for the 6- Month Primary Endpoint Follow-up period. Within each tabulation, subjects within the Safety Set that had a successful Scaffold implant will be tabulated separately.

The following tables will be produced:

- Topline Summary of All Safety Events
- AEs, SAEs by SOC, PT and Intensity
- ADEs, SADEs, and UADEs by PT and Intensity
- Safety Events of Interest by PT and Intensity

In addition, tables providing all AEs and SAEs by SOC, PT, and Intensity will be presented for the All Treated Set.

The calculation of safety event percent will be based on the number of subjects per safety event system organ class and preferred term, where:

Percent of Subjects Experiencing Each Safety Event =

$$\text{Number Subjects with Safety Event} * 100 / \text{Total Number of Subjects}$$

When tabulating a proportion, if a subject has multiple safety events classified to the same category, that subject will be tabulated once under the worst severity for that safety event category. Summary tables will be presented by seriousness and severity. All safety event information will be provided in data listings.

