5.4 Interim Evaluations and Primary Analysis

One interim evaluation was performed at the time the first 5 subjects received the Scaffold implant and completed the 6-month post-Scaffold implantation Follow-up Visit. The purpose of the interim evaluation was to support conversion of the pilot study into an HDE probable benefit study enrolling up to 36 subjects to achieve 20 subjects in the Primary Endpoint Analysis Set.

Subjects who received the Scaffold are to be followed for 24-months in clinic, and then the subjects will be followed annually by telephone contact for an additional 8 years. At the time of the last subject in the Primary Endpoint Analysis set completes the 6 Month Post-Implantation Visit, the Primary Analysis of all available data will be presented in tables, listings, and figures and a Clinical Study Report will be prepared. Data collected during the Long-term Follow-up will be reported via the format of Investigation Device Exemption (IDE) annual update.

A Data Safety Monitoring Board (DSMB) will be formed to evaluate safety and efficacy on an on-going basis. The DSMB will be notified of all serious safety events, safety events of interest, and study stopping rules. The DSMB may recommend that the study enrollment be put on hold or the study be terminated should safety events occur that are Scaffold-related and distinct from a safety event that may be associated with standard of care open spine surgery or sequelae considered part of the normal course of a non-penetrating SCI (contusion injury) following such surgery.

Additional safety reviews or ad-hoc analyses may be scheduled as recommended by the DSMB or the sponsor.

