6. STATISTICAL ANALYSIS METHODOLOGY

All data collected for this study will be presented in summary tables, listings, and figures (TLFs) as indicated in Appendix 1 of this SAP. Shells for TLFs with enough detail for programming will be provided as a guide to develop the programming SAS codes. These shells will be in sufficient detail to simulate the actual TLFs when they are created from the locked database.

The results will be presented primarily via data tabulation and listed by subject ID and time course because this is an HDE Probable Benefit study with a small sample size. Group descriptive statistics and cumulative statistics will be utilized if appropriate.

Tabulations for continuous data will use a standard set of summary statistics: number of observations available (n), mean, standard deviation (SD), median, and range (minimum, maximum).

Categorical or dichotomous data will be tabulated using counts and percentages. The numerator and denominator for each percentage calculation will be specified in the footnotes of table shells.

Data listings will present all information recorded in eCRFs and any derived variable(s) included in the analysis datasets for all subjects and visits.

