7.4 Statistical Conventions

7.4.1 Statistics Reported

- Unless otherwise specified, the mean and standard deviation (SD) will be displayed to one more decimal place than the original value, while minimum and maximum will be reported in the format of the original data, e.g.:

Original: xx

Mean and SD: xx.x

Minimum and maximum: xx

- Descriptive statistics in this template include: **Mean, Median, Standard Deviation (SD), Minimum, Maximum, and N**. In addition, 95% CI will be presented when appropriate.
- Unless specified in the actual TLF shells for a study, all percentages will be rounded to 1 decimal place in all tables/listings/figures. Rounding will take place after all calculations have been performed.
- Use of N versus n:
 - N = total number of subjects or subjects in the population.
 - n = total number of subjects or subjects in the specific category.

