Table 14.2.9.3	Number of Subjects With Improvements in QLI-SCI III - All Treated Set
Table 14.2.10.1	MRI - Observations of Edema and Hemorrhage - Safety Set Excluding Screen Failure Subjects Excluding Screen Failures
Table 14.2.10.2	MRI – Chronic Observations of Cyst and Spinal Cord Adhesion - Safety Set Excluding Screen Failure Subjects Excluding Screen Failures

Table 14.3.1.1	Topline Summary of All Safety Events - Safety Set Excluding Screen Failure Subjects Excluding Screen Failures
Table 14.3.1.2	Adverse Events by System Organ Class, Preferred Term, and Intensity - All Treated Set
Table 14.3.1.3.1	Summary of Adverse Events (AE) – 0-24 Months Post Implantation– Safety Set Excluding Screen Failure Subjects Excluding Screen Failures
Table 14.3.1.3.2	Summary of Adverse Events (AE) – 0-6 Months Post Implantation– Safety Set Excluding Screen Failure Subjects Excluding Screen Failures
Table 14.3.1.3.3	Summary of Adverse Events (AE) – 6-24 Months Post Implantation– Safety Set Excluding Screen Failure Subjects Excluding Screen Failures
Table 14.3.1.4.1	Summary of Adverse Device Effects (ADE) – 0-24 Months Post Implantation - Safety Set Excluding Screen Failure Subjects Excluding Screen Failures
Table 14.3.1.4.2	Summary of Adverse Device Effects (ADE) – 0-6 Months Post Implantation - Safety Set Excluding Screen Failure Subjects Excluding Screen Failures
Table 14.3.1.4.3	Summary of Adverse Device Effects (ADE) – 6-24 Months Post Implantation - Safety Set Excluding Screen Failure Subjects Excluding Screen Failures
Table 14.3.1.5.1	Summary of Safety Events of Interest – 0-24 Months Post Implantation - Safety Set Excluding Screen Failure Subjects Excluding Screen Failures
Table 14.3.1.5.2	Summary of Safety Events of Interest – 0-6 Months Post Implantation - Safety Set Excluding Screen Failure Subjects Excluding Screen Failures
Table 14.3.1.5.3	Summary of Safety Events of Interest – 6-24 Months Post Implantation - Safety Set Excluding Screen Failure Subjects Excluding Screen Failures
Table 14.3.1.6.1	Summary of Unanticipated Adverse Device Effect (UADE) – 0-24 Months Post Implantation - Safety Set Excluding Screen Failure Subjects Excluding Screen Failures
Table 14.3.1.6.2	Summary of Unanticipated Adverse Device Effect (UADE) – 0-6 Months Post Implantation - Safety Set Excluding Screen Failure Subjects Excluding Screen Failures

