Table 14.3.1.6.3	Summary of Unanticipated Adverse Device Effect (UADE) – 6-24 Months Post Implantation - Safety Set Excluding Screen Failure Subjects Excluding Screen Failures
Table 14.3.1.7.1	Summary of All Safety Events Leading to Discontinuation – 0-24 Months Post-Implantation - Safety Set Excluding Screen Failure Subjects Excluding Screen Failures
Table 14.3.1.7.2	Summary of All Safety Events Leading to Discontinuation – 0-6 Months Post-Implantation - Safety Set Excluding Screen Failure Subjects Excluding Screen Failures
Table 14.3.1.7.3	Summary of All Safety Events Leading to Discontinuation – 6-24 Months Post-Implantation - Safety Set Excluding Screen Failure Subjects Excluding Screen Failures
Table 14.3.2.1	Serious Adverse Events by System Organ Class, Preferred Term, and Intensity - All Treated Set
Table 14.3.2.2.1	Summary of Serious Adverse Events (SAE) – 0-24 Months Post Implantation -

	Safety Set Excluding Screen Failure Subjects Excluding Screen Failures
Table 14.3.2.2.2	Summary of Serious Adverse Events (SAE) – 0-6 Months Post Implantation - Safety Set Excluding Screen Failure Subjects Excluding Screen Failures
Table 14.3.2.2.3	Summary of Serious Adverse Events (SAE) – 6-24 Months Post Implantation - Safety Set Excluding Screen Failure Subjects Excluding Screen Failures
Table 14.3.2.3.1	Summary of Serious Adverse Device Effects (SADE) – 0-24 Months Post Implantation - Safety Set Excluding Screen Failure Subjects Excluding Screen Failures
Table 14.3.2.3.2	Summary of Serious Adverse Device Effects (SADE) – 0-6 Months Post Implantation - Safety Set Excluding Screen Failure Subjects Excluding Screen Failures
Table 14.3.2.3.3	Summary of Serious Adverse Device Effects (SADE) – 6-24 Months Post Implantation - Safety Set Excluding Screen Failure Subjects Excluding Screen Failures
Table 14.3.4.1.1	Subject Clinical Laboratory Values at Time Points - Safety Set Excluding Screen Failure Subjects Excluding Screen Failures
Table 14.3.4.1.2	Summary of Clinical Laboratory Tests and Changes from Baselines at Each Time Point - Low/Normal/High and - Clinical Significance - Safety Set Excluding Screen Failure Subjects Excluding Screen Failures
Table 14.3.4.1.3	Abnormal and Clinically Significant Chemistry Tests at Each Time Point - Safety Set Excluding Screen Failure Subjects Excluding Screen Failures
Table 14.3.4.2.1	Subject Hematology Values Across Time Points - Safety Set Excluding Screen Failure Subjects Excluding Screen Failures

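### The SAP's one safety percent formula gives the seven 6–24 month safety tables no denominator of subjects still followed, and the screen-failure and disposition outputs are assigned sets that do not fit them.

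*SAP*

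**What the plan says.** **Formula and set.** Section 6.3.2 gives one calculation, "Percent of Subjects Experiencing Each Safety Event": the number of subjects with the event, times 100, divided by the total number of subjects. Section 6.3 sets the population: "Safety analysis will be performed using all subjects in the Safety Population Excluding Screen Failure Subjects". Section 7.4.1 adds the notation "N = total number of subjects or subjects in the population". Section 6 leaves room for something else: "The numerator and denominator for each percentage calculation will be specified in the footnotes of table shells".

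**Periods.** The text of 6.3.2 names two: "Events will be tabulated for the overall study period and separately for the 6- Month Primary Endpoint Follow-up period". Appendix 9.1 has a third, for example "Summary of Adverse Events (AE) – 6-24 Months Post Implantation" and "Summary of Serious Adverse Events (SAE) – 6-24 Months Post Implantation", each on the Safety Set without screen failures.

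**Follow-up.** Section 5.4 states: "Subjects who received the Scaffold are to be followed for 24-months in clinic". Section 6.1.1 counts early withdrawals, and it counts unsuccessful implantations on a separate line from screen failures.

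**Sets for screening and disposition.** Section 5.1 limits the Safety Set to enrolled subjects who passed screening, yet splits its listings by screen-failure status. Section 6.1.1 treats the same set as everyone enrolled and asks for a count of screen failures. Section 5.1 assigns disposition to the Screened Set. In Appendix 9.1, Tables 14.1.1.2 (reasons for screen failure) and 14.1.1.3 (disposition) run on the Safety Set without screen failures, while Figure 14.1.1.3 runs on the Safety Set.

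**The concern.** A percentage in a table for months 6–24 invites reading as the risk of a late event among people observed in that window. A subject with no follow-up past month 6 cannot contribute a late event to the numerator but, under the formula as written, still counts in the denominator. Late adverse events, serious events and device effects would then look rarer than they were among subjects actually observed. In a single-arm device study with few subjects, a handful of such subjects can shift the figure by several percentage points.

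The set labels are a smaller matter of reporting. A table of reasons for screen failure has no rows if its population contains no screen failures, and a disposition table and figure drawn from different sets may not agree.

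**Working it through.** **1. Count the tables.** Appendix 9.1 lists these 6–24 month safety tables: 14.3.1.3.3 (AE), 14.3.1.4.3 (ADE), 14.3.1.5.3 (events of interest), 14.3.1.6.3 (UADE), 14.3.1.7.3 (discontinuation), 14.3.2.2.3 (SAE) and 14.3.2.3.3 (SADE). That is seven. The SAP contains one safety percent formula and no exception by period.

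**2. Algebra.** Let x be the subjects with a late event, R the subjects with follow-up past month 6, and N the subjects in the set.

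- Printed: 100·x/N
- Among followed subjects: 100·x/R
- Ratio, printed to followed: R/N

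**3. Can R be below N?** The SAP suggests three routes.

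- *Early withdrawals.* 6.1.1 counts them, and 6.2.1 has an imputation rule for subjects with no 6-month visit.
- *Unsuccessful implantations.* 6.1.1 lists them apart from screen failures, which suggests that they stay in N, while 5.4 states 24-month clinic follow-up only for Scaffold recipients.
- *Subjects only just at month 6 at the data cut.* 6.2.1 triggers the analysis when the 16th evaluable subject completes that visit.

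Section 6.3.2 also has implanted subjects tabulated separately. That removes only the second group.

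**4. Size.** The SAP gives no late-event figure to reproduce and neither R nor N. N is at least 16, the number meeting the Primary Endpoint Analysis Set criteria (3.2.1). The planned size of that set was 20. The planned enrolment cap of 36 is an outer limit, since enrolment by the SAP's definition also counts screen failures. Assume x = 3 and let the share not followed run from none to half:

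| N | Printed, 3/N | All followed | About 10% not followed | 25% not followed | 50% not followed |
|---|---|---|---|---|---|
| 16 | 18.8% | 18.8% (R=16) | 21.4% (R=14) | 25.0% (R=12) | 37.5% (R=8) |
| 20 | 15.0% | 15.0% (R=20) | 16.7% (R=18) | 20.0% (R=15) | 30.0% (R=10) |
| 36 | 8.3% | 8.3% (R=36) | 9.4% (R=32) | 11.1% (R=27) | 16.7% (R=18) |

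The last four columns are 3/R. Check for N = 20, R = 15: 20.0% × 15/20 = 15.0%, the printed value. Both x and the shares are assumptions.

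**5. Sets side by side.**

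| Output | Set assigned | Holds screen failures? |
|---|---|---|
| Disposition, 5.1 | Screened Set | Yes |
| Disposition, 6.1.1 | Starts from the Safety Set, read as all enrolled | Count requested |
| Table 14.1.1.3 | Safety Set without screen failures | No |
| Figure 14.1.1.3 | Safety Set | Unclear from 5.1 |
| Table 14.1.1.2 | Safety Set without screen failures | No, so empty as labelled |

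Disposition therefore has three sets, and the table of screen-failure reasons has a set with none in it.

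**The case against.** The strongest reply is section 6: denominators go into shell footnotes, and the shells are not shown. A suitable 6–24 month denominator may already be there. This stands, and it makes the denominator point conditional. Section 7.3.3 limits it somewhat: derivation rules belong in the SAP text rather than in footnotes. A footnote can name a denominator, but the rule for who counts as followed past month 6 is better fixed in 6.3.2.

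Second, the reader will have other information. Counts are printed beside percentages, disposition reports 12- and 24-month completers, 6.3.1 promises a summary of participation, and all events are listed. This softens the consequence but does not correct the percentage.

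Third, a reader might infer that at least one subject must lack late follow-up when the analysis is run. The text does not support that. Under 5.3 the lock comes after all subjects complete month 6 and the report is written, and the visit window is ±30 days, so the cut may fall later than the triggering visit. The protocol may also provide follow-up for non-implanted subjects.

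Fourth, the set labels look partly clerical. Many titles in Appendix 9.1 exclude screen failures twice over, which points to a global text replacement. Passing screening and later being classed a screen failure can also coexist, because 5.1 lets that status depend on eligibility checks at surgery. Both remarks explain the labels, but the labels still need correcting.

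**Conclusion.** The denominator point holds as a conditional one. As written, the formula understates late-event percentages by the factor R/N whenever some subjects lack follow-up past month 6 and the shells do not override it. The size is unknown and may be zero. The safety analysis is descriptive and the primary endpoint is untouched, so this is a correction worth making rather than a threat to the study's main conclusion. The set mismatch is of lower severity but does not depend on the shells: Table 14.1.1.2 is empty as labelled, and Table 14.1.1.3 omits the screen failures that 6.1.1 wants counted.

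Two stronger readings should not be drawn.

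- *Operated subjects could drop out of the safety tables*, because screen-failure status may be set at surgery. Section 5.1 does not say so, and 6.1.1 keeps unsuccessful implantations on a separate line.
- *Sections 5.4 and 6.3 conflict on when late data are analysed.* They can be read together: data available at the cut enter the Primary Analysis, later data go to the annual device updates, and further safety analyses remain optional. The 6–24 month period is simply not named in 6.3.2, which is an omission and not a contradiction.

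**What to change.** **In 6.3.2.** For the seven 6–24 month tables, take as denominator the subjects with safety follow-up beyond the 6-month visit at the data cut, and use the same boundary for the events counted. Print that number in the column header with those subjects' total follow-up time after month 6, so that subjects who have barely entered the window are visible. Name the 6–24 month period in the text beside the two already there. If the shells already use such a denominator, stating it in 6.3.2 is enough.

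**In 5.1, 6.1.1 and Appendix 9.1 (lower priority).** Run Tables 14.1.1.2 and 14.1.1.3 on the Screened Set and align Figure 14.1.1.3 with them. Reconcile the requirement in 5.1 that Safety Set members passed screening with the split by screen-failure status and with the all-enrolled description in 6.1.1.

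**Cost.** SAP wording and minor reprogramming. No new data are needed, since 4.5.1 already defines each subject's last study date and total days on study. Late percentages may come out higher and will be coarser: with R = 15, one subject is 100/15 = 6.7 points, against 100/20 = 5.0 points with N = 20.
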